Specific Aim 1: To evaluate the feasibility (recruitment, retention and adherence to therapy) and preliminary efficacy of local estrogen on vulvovaginal atrophy in the postpartum period.

Hypothesis: Use of low-dose vaginal estrogen in the postpartum period will decrease postpartum vaginal atrophy and associated symptoms.

We chose a validated measurement of vulvovaginal symptoms as our primary measure of vulvar atrophy. The Vaginal Vulvar Assessment Scale tools will be utilized during an exam at 6 weeks and 12 weeks. The tool also has a scale for physical exam findings associated with atrophy that will be recorded as well. Given most postpartum visits are scheduled at four to six weeks following a vaginal delivery for an uncomplicated

pregnancy and acute surgical wounds usually complete healing within two to four weeks, six weeks was deemed appropriate timing for vulvar assessment. The primary outcome for the study is Vulvar Assessment Scale (VuAS) at 6 weeks. Vaginal pH and maturation index will be obtained at follow up postpartum visits to further assess atrophy. Vaginal pH will be obtained in a standardized manner by swabbing indicator strips with pH range of 4.0 to 7.5 against the distal posterior vagina and interpreted by the examiner. Vaginal maturation will also be obtained via vaginal smears at the introitus and sent for quantitative assessment. Presence of granulation tissue and visible healing abnormalities such as suture line disruption, visible sutures, abscess, hematoma, and need for reoperation will be noted.

Specific Aim 2: To estimate the effect of local vaginal estrogen in the postpartum period on perineal pain, quality of life, and sexual function.

Hypothesis: Use of low-dose vaginal estrogen in the postpartum period will improve vaginal and perineal pain, quality of life measures and sexual function.

These will be assessed using validated questionnaires consisting of a visual analog scale for pain (VAS), Edinburgh Postnatal Depression Scale (EPDS), the Urinary Distress Inventory-6 (UDI-6), the Fecal Incontinence Severity Index for bowel symptoms (FISI), and the Female Sexual Function Index (FSFI). These questionnaires will be completed on day of randomization and postpart um visits at 6 weeks and 12 weeks.

Specific Aim 3: To compare patient satisfaction, ease of product use, likelihood of continued use, and rates of adverse events for the vaginal estrogen and placebo groups.

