Hypothesis: Use of low-dose vaginal estrogen in the postpartum period will have a higher treatment satisfaction rate when compared with placebo. The rate of adverse events between the groups will be similarly minimal.

We will use a Likert scale to assess patient satisfaction, ease of product use, comfort, and likelihood of continued use. We will monitor for adverse events related or possibly related to local estrogen. All local estrogen and non-local estrogen adverse events will be recorded.

Impact: There is limited knowledge of dyspareunia and perineal pain postpartum and the role of vulvar and vaginal atrophy. Increased efforts to measure and improve postpartum sexual functioning can impact a substantial number of women suffering from these oftentimes lengthy symptoms. Given the psychological burden a patient can endure from pelvic floor pain, it is important investigate tre atment options for women with perineal trauma in the postpartum period.

RESEARCH STRATEGY

A.SIGNIFICANCE

The postpartum period is a challenging time that requires a balance of physical, social, and psychological changes. It is characterized by such challenges as lack of sleep, fatigue, pain, breastfeeding, depression, stress, lack of sexual desire and urinary incontinence.³ The majority of women in the United States do not interact with a health care provider after discharge until the first postpartum visit 4 to 6 weeks following delivery. Because of this, many postpartum complaints may not be addressed in the limited time available. The postpartum period is not well defined but considered to last between 4 to 6 weeks following delivery during which anatomical and physiological changes return to the non-pregnant state.⁴ This time frame likely represents historical traditions, as studies have demonstrated peripartum effects are present months after delivery.⁵ Evidence-based studies of optimal maternal postpartum management are lacking and clinical recommendations are often based on expert opinion and observational studies.⁶ Recent data on urinary and

sexual functioning postpartum have been important in investigating some of the health domains significant to women during this period.⁷

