In order to effectively evaluate the impact of each group on satisfaction and ease of product use and likelihood of continued use of vaginal estrogen and placebo group, we will administer global rating scales. Global ratings of satisfaction have previously been found to have acceptable validity for measuring outcomes in studies of treatment for urinary incontinence.

Research Design

1. Satisfaction and ease of use: These outcomes will be assessed with Likert scales collected via RedCap at weeks 6 and 12. Satisfaction will be assessed using the patient satisfaction questionnaire, with responses of "completely," "somewhat," and "not at all," in response to the question, "How satisfied were you with your progress with this treatment?" In a similar fashion, ease of usability will be scored be assessed on a score of 0, 1, 2, 3, 4, 5, and 6, correlating to the following responses of "strongly disagree," "disagree," "slightly disagree," neither agree nor disagree", "slightly agree," "agree," "strongly agree" to the statement, "This product was easy to use."

2. Likelihood of continued use: This will be assessed at the end of the study intervention with a 7-point Likert scale at weeks 6 and 12. This will be assessed on a score of 0, 1, 2, 3, 4, 5, and 6, correlating to the following responses of "strongly disagree," "disagree," "slightly disagree," neither agree nor disagree", "slightly agree," "agree," "strongly agree" to the statement, "I plan to continue using this product."

3. Adverse events (AEs): Potential AEs of interest include vaginal pain attributed to cream placement, vaginal infection, wound separation, and urinary tract infection. Breast myalgia and breastfeeding practices will be noted. Participants will be instructed to call and report any/all adverse events to research personnel and clinical staff. All AEs will be reported to the IRB of the institution at which the AE occurred, recorded in the research database and if needed the patient will be seen for a clinical assessment. At each clinical/research visit the participant will be asked about any adverse events. AEs will be reported with study outcomes.

Questionnaires will be administered to vaginal estrogen and placebo groups at clinic encounters at 6 weeks and 12 weeks. See Fig 1.

Statistical Analysis

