Similar to analyses proposed in Aim 1, secondary endpoints will be analyzed via generalized linear mixed models or linear generalized estimating equation models (GEE), adjusting for stratification factors and accounting for correlation over time.

Anticipated results

Assuming an improvement in perineal symptoms associated with vulvar atrophy with local estrogen use, patients will have higher scores in satisfaction and likelihood of continued use compared to placebo group. Ease of use global rating will likely be similar in vaginal estrogen and placebo groups.

Pitfalls and Solutions

Again retention and compliance is a concern in the postpartum period. Strategies including telephone and text reminders will be utilized. If patients are unable to attend their follow-up visit, a study member will call the patient and record the patient's responses.

D. RIGOR AND REPRODUCIBILITY

All participants will be postpartum women with a perineal laceration following a vaginal delivery at Wexner Medical Center. Wexner Medical Center has approximately 5,000 deliveries per year. It is a large, multidisciplinary academic medical center that delivers superior quality care to a diverse urban population of patients. Columbus, Ohio is the fifteenth largest city in the United States and is home to a population representing 134 nations and speaking 105 languages. In addition, The Ohio State University (OSU) Divisions of Obstetrics and Gynecology represents a diverse team of faculty, residents, and fellows dedicated towards improving women's health through evidence-based care, research, and education. As an institution, OSU Wexner Medical Center has long been supportive of leadership in research and excellence in patient care.

Estrace® cream is currently available for the treatment of genitourinary symptoms of menopause. We anticipate other clinicians will have similar results in their population.

E. HUMAN SUBJECTS

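### Aim 3's single generic model sentence is a poor fit for rare adverse events and leaves the hypothesised satisfaction rate undefined

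*Combined protocol and SAP*

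**What the plan says.** Specific Aim 3 is "To compare patient satisfaction, ease of product use, likelihood of continued use, and rates of adverse events" in the two groups. Its hypothesis is that vaginal estrogen "will have a higher treatment satisfaction rate when compared with placebo". On safety it adds: "The rate of adverse events between the groups will be similarly minimal".

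Under Research Design for Aim 3, satisfaction is a single question "with responses of 'completely,' 'somewhat,' and 'not at all". These levels have no numeric coding and no cut-off. Ease of use and continued use are 7-point items scored 0 to 6. For safety, "Potential AEs of interest include vaginal pain attributed to cream placement, vaginal infection, wound separation, and urinary tract infection", and "AEs will be reported with study outcomes".

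The Statistical Analysis paragraph for Aim 3 repeats the Aim 2 sentence: "secondary endpoints will be analyzed via generalized linear mixed models or linear generalized estimating equation models (GEE", with adjustment for stratification and for correlation over time. It gives no link or distribution by outcome type, no effect measure and no rule for few or no events. The Anticipated results paragraph then says that "patients will have higher scores in satisfaction and likelihood of continued use compared to placebo group".

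**The concern.** One sentence written for repeated questionnaire scores also has to serve rare yes/no events and a three-level item.

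- **Adverse events.** With few events and small arms, an arm with no events of a given type is a realistic outcome. The plan does not say what is then reported. The limit that matters most for safety, how large an excess risk the data still allow, is the one that a Wald-type interval is likely to understate.
- **Satisfaction.** The hypothesis is about a rate and the expected result is about scores. Without a definition, the analyst chooses the quantity after the data are in.

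Safety and acceptability are among the results that a pilot most needs to report dependably.

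**Working it through.** **Inputs.** Sample size determination: 70 randomised 1:1, so 35 per arm; with 20% attrition, 35 × 0.8 = 28 per arm. Adverse event risk: no figure is given. I read *minimal* as 2–5% per woman for a given event type (assumption) and show 1–15%. The documents state no figure for Aim 3, so there is none to reproduce.

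**1. How often is exactly one arm empty?** With equal risk p and n per arm, q = (1 − p)^n is the chance that an arm has no events, and P(exactly one empty) = 2q(1 − q).

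| p | q, n = 28 | P, n = 28 | q, n = 35 | P, n = 35 |
|---|---|---|---|---|
| 1% | 0.755 | 37% | 0.703 | 42% |
| 2% | 0.568 | 49% | 0.493 | 50% |
| 3% | 0.426 | 49% | 0.344 | 45% |
| 5% | 0.238 | 36% | 0.166 | 28% |
| 10% | 0.052 | 10% | 0.025 | 5% |
| 15% | 0.011 | 2% | 0.003 | 1% |

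**2. What do the named methods return?** Take 4/28 against 0/28.

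- *Logit link.* The log odds in the empty arm have no finite estimate. On constructed two-visit data the ordinary logistic fit was singular, and a logit GEE printed a log odds ratio of 24.0 with SE 0.50, which means nothing. No logistic mixed model was fitted; the empty cell causes the same problem there.
- *Linear GEE.* It gives a finite answer: 4/56 = 7.1 points per visit, 95% CI 0.7 to 13.6.
- *Per woman, Wald.* Difference 4/28 = 14.3 points; SE = √(0.143 × 0.857/28 + 0) = 6.6 points; 95% CI 14.3 ± 1.96 × 6.6 = 1.3 to 27.2. The empty arm adds nothing to this variance.
- *Per woman, Newcombe.* 95% CI −0.5 to 31.5.

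**3. Coverage when risks differ.** I enumerated all pairs of binomial counts at true risks of 5% and 2% (both assumed), using unadjusted intervals.

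| Interval | n = 28 | n = 35 |
|---|---|---|
| 95% Wald | 83% | 83% |
| 95% Newcombe | 99.8% | 99.1% |
| 90% Wald | 73% | 82% |
| 90% Newcombe | 97% | 96% |

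Much of the Wald shortfall comes from trials with no events in either arm. Their probability is 0.238 × 0.568 = 13.5% at 28 per arm and 0.166 × 0.493 = 8.2% at 35. There the Wald interval has zero width and counts as a miss; a linear GEE on constructed 0 v 0 data returned an error. Among the remaining trials, 95% Wald coverage is 0.83/0.865, about 96%, at 28 per arm and 0.83/0.918, about 90%, at 35. For 0 v 0 at 28 per arm Newcombe gives ±z²/(n + z²) = ±3.84/31.84 = ±12.1 points.

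**4. Is the test inflated when risks are equal?** Rejection rates at nominal 10%, with 0 v 0 counted as no rejection:

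| p | Wald, n = 28 | Wald, n = 35 |
|---|---|---|
| 2% | 2.1% | 3.3% |
| 3% | 4.4% | 6.3% |
| 5% | 8.6% | 10.3% |

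At 10% risk the Wald rate is 11.4–11.7%. Over 2–5% risk, Fisher's test rejects in 0.02–0.6% of trials (28 per arm) and 0.06–1.1% (35 per arm).

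**5. Satisfaction.** Code the three levels 0/1/2, lowest to highest. Distributions (20%, 20%, 60%) and (0%, 60%, 40%) have means 0.20 + 1.20 = 1.4 and 0.60 + 0.80 = 1.4. Yet the proportion completely satisfied is 60% against 40%, and the proportion at least somewhat satisfied is 80% against 100%. The mean difference is zero, while the two possible rates differ by 20 points in opposite directions.

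**The case against.** The case on the other side is substantial, and much of it stands.

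- *A reader might infer that linear GEE breaks down when one arm is empty.* It does not; it returned an error only at 0 v 0. With stratum adjustment, as planned, the empty arm's fitted mean also has a non-zero SE.
- *A reader might infer that chance splits will be declared significant too often.* Step 4 does not support that at equal risks of 2–5%. Most one-empty-arm trials are 1 v 0 or 2 v 0, with Wald p of 0.31 and 0.14 at 28 per arm; three or more against none has probability only 2–8%. Setting the Wald p of 0.031 for 4 v 0 against Fisher's 0.11 mostly shows how conservative Fisher's test is. The plan's 10% error rate is also stated for VuAS only.
- *A reader might infer that adverse event results will be missing, or that every event must go through these models.* Per-arm counts can still be reported with the study outcomes. The secondary-outcome list under Evaluation Criteria and Progress omits adverse events, so whether the model sentence covers them is unclear. But Aim 3 promises a comparison of rates, and no other comparison method is given.
- *A reader might infer that the named model class cannot give a satisfaction rate.* Generalized mixed models include binary and cumulative-logit models. What is missing is the link and the cut-off.
- *Scope.* Healing abnormalities are Aim 1 examination findings, and the 7-point items have no zero-event problem. Neither belongs in this point.

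**Conclusion.** The point holds in limited form. For adverse events, if risks are about 2–5% per type, one arm will be empty and the other not in 28–50% of trials. The plan then offers a logit model with no finite estimate or a linear GEE whose interval can be too narrow. The coverage figure (about 83% at 2% against 5%) rests on assumed risks, on an unadjusted Wald interval standing in for the planned adjusted GEE, and on counting trials without any event as misses. The problem of one empty arm fades at risks of 10% and above. The weakness lies in the interval, not in an excess of false positives.

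For satisfaction, the gap needs no assumed rate: the hypothesis names a rate that the plan does not define, and a mean-score contrast does not estimate it.

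Both are worth correcting, because they concern safety and acceptability and cost little. Neither affects the primary VuAS analysis.

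**What to change.** 1. **Adverse events.** Use one record per woman for each event type (any event by week 6; any event by week 12). Report counts per arm and the risk difference with a Newcombe or Miettinen-Nurminen interval, in place of the mixed model or linear GEE. Treat any exact test as supportive only, because it is very conservative at these rates.
2. **Satisfaction.** Fix in advance which response counts as satisfied, for example the top level, and estimate the between-arm difference in that proportion. Use the same term in the hypothesis and the anticipated results.
3. **7-point items.** No change is needed; the planned models can stay.

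The cost is SAP wording. Adverse event intervals will be wider, and the repeated-visit model is given up for those outcomes.
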